## Revision History

Document Revision Number	Template Number and Version	Section	Change	Reason for Change
Version: AA	90702621 Rev/Ver AE	Initial release	NA	NA
Version: AB	90702621 Rev/Ver AE	Section :4.1	Corrected the definition of analysis set	Sponsor corrections

## 1 PROTOCOL SUMMARY

A Prospective, Multi-center, Non-Randomized Controlled Trial for A Novel Facilitated Antegrade Steering Technique in Revascularization of Coronary Chronic Total Occlusions In China Population(FAST-CTO China)	
Objective(s)	To assess the safety and efficacy of the Bridge Point CTO system in recanalization of CTO lesions in a multicenter study in Chinese population
Planned Indication(s) for Use	All subjects who are candidates for percutaneous coronary intervention (PCI), signed the informed consent form and had chronic total coronary occlusion (CTO) lesion will be evaluated for enrollment in this study.
Test Device	BridgePoint CTO System: 
 
• CrossBoss Catheter
 
• Stingray LP Catheter
 
• Stingray Guidewire and Extension Wire
 

Control Device	NA
Study Design	Prospective, multicenter, single-arm, observational study
Planned Number of Subjects	At least 100 subjects will be enrolled. Each site will be allowed to enroll up to a maximum of 25 subjects.
Planned Number of Centers / Countries	Up to 10 investigational sites in China
Primary Safety Endpoint:	30-day MACE rate for CTO cases in which the BridgePoint Medical System was used. MACE is defined as the composite of cardiac death, Q-wave and non-Q-wave myocardial infarction(MI), and any ischemia-driven target lesion revascularization(TLR).
Primary Effectiveness Endpoint:	Technical Success: the ability of the BridgePoint Medical System to successfully facilitate placement of a guidewire beyond a CTO lesion in the true vessel lumen/within the collaterals
Secondary Endpoints	
 
• Procedural success is a mean lesion diameter stenosis <50% in 2 near-orthogonal projections with TIMI 2-3 flow, as visually assessed by the physician, without the occurrence of in-hospital Q wave MI, TLR, or cardiac death.
 
• Total procedure time
 
• Total Fluoroscopy time and dose (mSv)
 
• Total contrast dose
 
• rate of MACE at 30 days, 6 months and 12 months
 
• rate of stent thrombosis (ST) at 30 days, 6 months and 12 months
 
• rate of cardiac tamponade through hospital discharge after the index procedure
 
• rate of kidney failure caused by contrast through hospital discharge after
 

	the index procedure
Method of Assigning Patients to Treatment	NA
Follow-up Schedule	Subject follow up will occur via telephone contact or clinic visit at 30 days, 6and 12 months post index procedure, for all enrolled subjects.
Study Duration	About 2 years.
Required Medication Therapy	
Based on the American College of Cardiology (ACC)/American Heart Association (AHA)/Society for Cardiovascular Angiography and Interventions (SCAI) guidelines and supported by the European Society of Cardiology (ESC) guidelines, dual antiplatelet therapy with aspirin and a clopidogrel is prescribed as follows to reduce the risk of thrombosis.
 
Aspirin:
 
 
For subjects who have been taking aspirin for <math>\geq</math> 72 hours at the time of the procedure, a loading dose is not required. But a 75-325 mg aspirin is recommended prior to the index procedure.
 
For subjects who have not been taking aspirin for <math>\geq</math> 72 hours at the time of the procedure, a loading dose is recommended 24 hours prior to the index procedure, where the loading dose shall be decided by the investigator.
 
Subjects shall take aspirin indefinitely after the index procedure.
 
 
Thienopyridine
 
 
For subjects who have been taking clopidogrel for <math>\geq</math> 72 hours at the time of the index procedure, a loading dose is not required.
 
For subjects who have not been taking clopidogrel for <math>\geq</math> 72 hours at the time of the index procedure, a loading dose is required. It is recommended that the loading dose be administered prior to the index procedure. However, in all cases, the loading dose is required to be administered not more than2 hours after the index procedure.
 
 
The following loading doses are recommended:
 
Clopidogrel
 
 
A peri-procedural loading dose of 600 mg is recommended.
 
Subjects must be treated with clopidogrel for at least 6 months following the index procedure. In subjects not at high risk of bleeding, clopidogrel treatment should continue for at least 12 months following the index procedure.
 

Key Inclusion Criteria	
Clinical Inclusion Criteria:
 
CI1. Subject must be <math>\geq 18</math> but <math>< 80</math> years of age
 
CI2. Subject (or legal guardian) understands the trial requirements and the treatment procedures and provides written informed consent before any trial-specific tests or procedures are performed
 
CI3. Subject is eligible for percutaneous coronary intervention (PCI)
 
CI4. Subject has symptomatic coronary artery disease or myocardial infarction (MI) with objective evidence of ischemia or silent ischemia
 
CI5. Subject is an acceptable candidate for coronary artery bypass grafting (CABG)
 
CI6. Subject is willing to comply with all protocol-required follow-up evaluation
 
CI7. Subject has a left ventricular ejection fraction (LVEF) <math>\geq 45\%</math> as measured within 60 days prior to enrollment
 
Angiographic Inclusion Criteria:
 
AI1. A maximum of one de novo CTO lesion in a native coronary artery with thrombolysis in Myocardial Infarction (TIMI) flow grade 0
 
AI2. Non-acute CTO lesion with an estimated duration of at least 3 months by clinical history and/or comparison with previous angiogram or electrocardiogram(ECG)
 
AI3. The CTO lesion must have an angiographic landing zone <math>\geq 10</math> mm proximal to any major bifurcation without severe calcification.
 
AI4. Lesion length <math>< 40</math>mm without excessive tortuosity and angulation(<math>>45^\circ</math>)

Key Exclusion Criteria	
Clinical Exclusion Criteria:
 
CE1. Subject has clinical symptoms and/or ECG changes consistent with Acute MI(include STEMI and Non- STEMI) within 1 week
 
CE2. Subject has cardiogenic shock, hemodynamic instability requiring inotropic or mechanical circulatory support, intractable ventricular arrhythmias, or ongoing intractable angina.
 
CE3. Subject has received an organ transplant or is on a waiting list for an organ transplant
 
CE4. Subject is receiving or scheduled to receive chemotherapy within 30 days before or after the index procedure
 
CE5. Planned PCI (including staged procedures) or CABG after the index procedure
 
CE6. Subject has a known allergy to contrast (that cannot be adequately pre-medicated)and/or protocol-required concomitant medications (e.g., aspirin or all thienopyridines)
 
CE7. Subject has one of the following (as assessed prior to the index procedure):
 

• Other serious medical illness (e.g., cancer, congestive heart failure) with estimated life expectancy of less than 12 months

• Current problems with substance abuse (e.g., alcohol, cocaine, heroin, etc.)

	

• Planned procedure that may cause non-compliance with the protocol or confound data interpretation

 
CE8. Subject is receiving chronic (<math>\geq 72</math> hours) anticoagulation therapy (i.e., heparin, coumadin)
 
CE9. Subject with out of range complete blood count (CBC) values that are determined by the study physician to be clinically significant.
 
CE10. Subject has documented or suspected liver disease, including laboratory evidence of hepatitis
 
CE11. Subject is on dialysis or has baseline serum creatinine level <math>>2.0</math> mg/dL (177<math>\mu</math>mol/L)
 
CE12. Subject has a history of bleeding diathesis or coagulopathy or will refuse blood transfusions
 
CE13. Subject has had a history of cerebrovascular accident (CVA) or transient ischemic attack (TIA) within the past 6 months
 
CE14. Subject has an active peptic ulcer or active gastrointestinal (GI) bleeding
 
CE15. Subject has signs or symptoms of active heart failure (i.e., NYHA class IV) or LVEF <math>< 45\%</math> at the time of the index procedure
 
CE16. Subject is participating in another investigational drug or device clinical trial that has not reached its primary endpoint or intends to participate in another investigational drug or device clinical trial within 12 months after the index procedure
 
CE17. Subject had PCI within the previous 2 weeks
 
CE18. Subject with known intention to procreate within 12 months after the index procedure (women of child-bearing potential who are sexually active must agree to use a reliable method of contraception from the time of screening through 12 months after the index procedure)
 
CE19. Subject is a woman who is pregnant or nursing (a pregnancy test must be performed within 7 days prior to the index procedure in women of child-bearing potential)

	
Angiographic Exclusion Criteria:
 
AE1. Target lesion is an aorto-ostial lesion or located in left main coronary artery, previous venous or arterial bypass grafts
 
AE2. Target lesion involving a segment of previous stent
 
AE3. Target vessel has excessive tortuosity and/or angulation proximal to the target lesion(<math>>45^\circ</math>)
 
AE4. Target lesion and/or the target vessel proximal to the target lesion is moderately to severely calcified by visual estimate
 
AE5. Target lesion is located within 5 mm of the origin of the left anterior descending (LAD) coronary artery or left circumflex (LCx) coronary artery by visual estimate
 
AE6. Target lesion will be accessed via a saphenous vein graft or arterial graft

	
AE7. Subject has unprotected left main coronary artery disease (>50% diameter stenosis)
 
AE8. Thrombus, or possible thrombus, present in the target vessel (by visual estimate)
 
AE9. Target vessel has a dissection greater than National Heart, Lung, Blood Institute (NHLBI) type C

Statistical Methods	
Primary Statistical Hypothesis	There is no formal statistical hypothesis for this observational, single-arm study. In order to support the stated objectives, the sample size for this trial will be approximately 100 subjects. Descriptive statistics will be performed for key variables collected in the study. The detail will be documented in the statistical analysis plan.
Safety Parameters	All serious adverse events (SAE), adverse device effects (ADE), major adverse cardiac events (MACE) and stent thrombosis will be collected up to 12months follow-up intervals. A clinical events committee (CEC) will adjudicate for MACE and stent thrombosis through the 12-month follow-up.

## 2 INTRODUCTION

This statistical analysis plan addresses the planned analyses for A Novel Facilitated Antegrade Steering Technique in Revascularization of Coronary Chronic Total Occlusions in China Population (FAST-CTO China) based on protocol version AC dated 12 Nov 2019. Specified analyses may be used for scientific presentations and/or manuscripts, and regulatory submissions. It is a prospective, non-randomized, single-arm and multi-center post-marketing observational study, intended to collect intraoperative and postoperative clinical data of BridgePoint CTO Medical System in the revascularization of CTO lesions in China's real world settings. The Primary analysis will be based on 30 days post procedure. The study requires follow-up via telephone or clinical visit at the following time points: 30 days, 6 months and 12 months after the index procedure.

## 3 ENDPOINT ANALYSIS

All primary and secondary study endpoints will be assessed on the basis of intention to treat, i.e., analyzing all subjects who received BridgePoint CTO Medical System devices.

### 3.1 Primary Safety Endpoint

30-day MACE rate for CTO cases in which the BridgePoint Medical System was used.

MACE is defined as the composite of cardiac death, Q-wave and non-Q-wave myocardial infarction(MI), and any ischemia-driven target lesion revascularization(TLR).

The primary endpoint is summarized with counts and percentage and based on binomial proportion 95% CI will be presented for 30-day MACE and thus summarized based on the MACE definition by Cardiac death, Myocardial Infarction, Target Vessel Revascularization. The endpoint will be analyzed based on both ITT and PP population definitions.

#### 3.1.1 Hypotheses

There is no specific hypothesis planned for this study.

#### 3.1.2 Sample Size

The study planned to enroll 100 patients with CTO lesions and will use BridgePoint Medical CTO System for treatment.

#### 3.1.3 Statistical Methods

For Primary safety endpoints, we calculate the 30-day Mace rate using the Continuous variables (mean, standard deviation, observation number, minimum and maximum, 95% Confidence Interval).

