11.3.2 Data Analysis

Continuous variables (mean, standard deviation, observation number, minimum and maximum) and discontinuous variables (percentage and number of events / number of samples) of baseline and clinical outcome variables will be summarized by descriptive statistics.

This study will collect patient follow-up information during and post procedure, at hospital discharge or at 30 days, 6 months and 12 months post procedure as described in the clinical trial schedule, using descriptive statistics to summarize continuous variables such as procedure time and X-ray time (such as mean, standard deviation, observed value, minimum and maximum value) and discontinuous variables (frequency table or percentage).

Clinical event rate will be expressed by percentage, and continuous variables will be expressed by number of samples, mean value, standard deviation, minimum and maximum value, where point estimation and 95% confidence limit will be provided.

12 Data Management

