### **3.2 Primary Effectiveness Endpoint**

It is the Technical Success, the ability of the BridgePoint Medical System to successfully facilitate placement of a guidewire beyond a CTO lesion in the true vessel lumen/within the collaterals

The primary endpoint is summarized with counts and percentage and based on binomial proportion 95% CI will be presented for successfully facilitate placement of a guidewire and thus summarized. The endpoint will be analyzed based on both ITT and PP population definitions.

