#### **3.2.3 Statistical Methods**

For Calculating the Primary Effectiveness, the discontinuous variables (percentage and number of events / number of samples) of baseline and clinical outcome variables will be summarized by descriptive statistics and for continuous variables (mean, standard deviation, observation number, minimum and maximum, 95% Confidence Interval) will be calculated.

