### **3.3 Secondary Endpoint**

The Secondary endpoints will be analyzed for all subjects at 30day, 6months, 12months and a one year follow up will be done for:

- Procedural success is a mean lesion diameter stenosis <50% in 2 near-orthogonal projections with TIMI 2-3 flow, as visually assessed by the physician, without the occurrence of in-hospital Q wave MI, TLR, or cardiac death.
- Total procedure time
- Total Fluoroscopy time and dose (mSv)
- Total contrast dose
- rate of MACE at 30 days, 6 months and 12 months
- rate of stent thrombosis (ST) at 30 days, 6 months and 12 months
- rate of cardiac tamponade through hospital discharge after the index procedure
- rate of kidney failure caused by contrast through hospital discharge after the index procedure

Secondary endpoint analysis are analyzed with both Intent to treat and per-protocol analysis and summarized with counts and percentage and based on binomial proportion 95% CI will be presented.

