### **5.11 Other Analyses**

Clinical event rate will be expressed by percentage, and continuous variables will be expressed by number of samples, mean value, standard deviation, minimum and maximum value, where point estimation and 95% confidence limit will be provided.

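### SAP 3.1.3 gives continuous-variable statistics for the yes/no 30-day MACE rate, against SAP 3.1, and SAP 3.1 lists TVR as a MACE component although MACE counts only ischemia-driven TLR

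*SAP*

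**What the plan says.** The SAP describes the analysis of 30-day MACE twice.

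- SAP 3.1 (Primary Safety Endpoint) plans counts and a percentage, and says that an interval "based on binomial proportion 95% CI will be presented for 30-day MACE".
- SAP 3.1.3 (Statistical Methods for the same endpoint) says "we calculate the 30-day Mace rate using the Continuous variables (mean, standard deviation, observation number, minimum and maximum, 95% Confidence Interval".

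The general rules agree with SAP 3.1. SAP 5.11 states "Clinical event rate will be expressed by percentage" and treats continuous variables separately; Protocol 11.3.2 has the same sentence. The parallel methods section for technical success, SAP 3.2.3, lists continuous statistics too, but it also includes "discontinuous variables (percentage and number of events / number of samples", which SAP 3.1.3 does not.

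SAP 3.2 and 3.3 also plan a binomial 95% CI, for technical success and the secondary endpoints. Neither document names the type of interval.

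On the components, SAP 3.1 and Protocol 7.1 define MACE as cardiac death, Q-wave or non-Q-wave MI, and ischemia-driven TLR. SAP 3.1 then says the endpoint is "summarized based on the MACE definition by Cardiac death, Myocardial Infarction, Target Vessel Revascularization".

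**The concern.** There are two separate faults.

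**Summary method.** Mean, SD, minimum and maximum are not informative for a 0/1 outcome. The minimum and maximum will be 0 and 1 unless every subject has the same result, and the SD is fixed by the proportion. What can change is the confidence interval. A programmer working from SAP 3.1.3 could build it from the mean and SD. One working from SAP 3.1 could take the unnamed binomial interval as Wald. Both perform poorly when events are few, and they err mainly towards an upper limit that is too low, which makes the device look safer than the data support. In a single-arm study with no hypothesis, this interval is all the reader has for judging uncertainty in the primary safety rate.

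**Component label.** Protocol 31.2 defines TVR as either TLR or remote TVR, and remote TVR excludes the target lesion. If TVR is tabulated as a MACE component, a subject with only a remote TVR would appear in the breakdown without being a MACE case, and the table might not reconcile with the composite.

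**Working it through.** **Inputs**

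- n = 100 (SAP 3.1.2), assuming complete 30-day data.
- A two-sided 95% interval (assumed; the SAP gives only the level).
- True MACE rate: the plan states none for this trial, so 1% to 8.5% is assumed. The earlier FAST-CTO trial in Protocol 4.3.3.3 had 7/147 = 4.8%, used here only as illustration.

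The plan has no figure of its own to reproduce on this point.

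**Formulas**, with x events and p = x/100

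- Mean/SD: SD = √(100·p(1−p)/99); limits p ± 1.984·SD/10, where 1.984 is the 97.5% t quantile on 99 df. SAP 3.1.3 gives no CI formula, so this is an assumed literal reading.
- Wald: p ± 1.96·√(p(1−p)/100).
- Exact (Clopper-Pearson): lower limit = 2.5% quantile of Beta(x, 101−x), set to 0 at x = 0; upper limit = 97.5% quantile of Beta(x+1, 100−x).
- Wilson: the score interval.

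Example with 5/100: SD = √(100 × 0.05 × 0.95/99) = 0.219, so mean/SD gives 0.05 ± 1.984 × 0.0219 = 0.65% to 9.35%.

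| Events | Mean/SD | Wald | Wilson | Exact |
|---|---|---|---|---|
| 0/100 | 0 to 0% | 0 to 0% | 0 to 3.70% | 0 to 3.62% |
| 2/100 | −0.79 to 4.79% | −0.74 to 4.74% | 0.55 to 7.00% | 0.24 to 7.04% |
| 5/100 | 0.65 to 9.35% | 0.73 to 9.27% | 2.15 to 11.18% | 1.64 to 11.28% |
| 77/100 | 68.6 to 85.4% | 68.8 to 85.3% | 67.9 to 84.2% | 67.5 to 84.8% |

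The last row stands for technical success, where the choice hardly matters.

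**Coverage** at true rate r is the sum of the Binomial(100, r) probabilities over those x whose interval contains r.

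| True rate | Mean/SD | Wald | Wilson | Exact |
|---|---|---|---|---|
| 1% | 63.3% | 63.3% | 92.1% | 98.2% |
| 2% | 86.6% | 86.6% | 94.9% | 98.5% |
| 3% | 80.2% | 80.2% | 96.9% | 98.9% |
| 4.8% | 86.1% | 85.5% | 94.1% | 97.1% |
| 7% | 91.6% | 91.6% | 97.2% | 97.2% |
| 8.5% | 92.4% | 92.4% | 93.1% | 97.1% |

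The 63.3% at 1% arises because P(0 events) = 0.99^100 = 36.6%, and with 0 events the interval is 0–0%. At 4.8%, the mean/SD upper limit with 2 events is 4.79%, so 0, 1 or 2 events all miss on the low side.

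The probability that the mean/SD upper limit falls below the truth is 13.3%, 19.5%, 13.6% and 7.4% at true rates of 2%, 3%, 4.8% and 7%; the nominal value is 2.5%.

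Coverage jumps between neighbouring rates, so it was also computed on a grid of step 0.01 percentage points from 2% to 7%:

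- mean/SD 80.1–95.4%, average 90.4%
- Wald 79.6–94.7%, average 90.1%
- Wilson 92.7–97.8%, average 95.6%
- exact 95.4–99.3%

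**Component label.** No arithmetic applies. MACE (SAP 3.1, Protocol 7.1) contains TLR; the SAP 3.1 breakdown contains TVR; Protocol 31.2 makes TVR equal to TLR plus remote TVR. The breakdown is therefore wider than the composite by the remote TVR events. The documents give no basis for estimating how many there would be.

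**The case against.** The best reply is that the plan can be read correctly. SAP 3.1 is the parent section and asks for a binomial interval, which a mean/SD interval is not. SAP 3.1.3 gives no formula and can be read with it. It looks like the text of SAP 3.2.3 with the percentage half dropped. What then remains is an unnamed binomial interval, which does harm only if Wald is chosen. The 63% coverage needs an assumed true rate of 1%, well below the 4.8% of the earlier trials. No hypothesis or threshold is at stake, and the difference at 5/100 is about two percentage points. As for TVR, the composite is stated with TLR in the same section, and the label may simply echo the clinical events committee's remit, which Protocol 27.3 gives as TVR, MI and death.

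Much of this stands. The intent is recoverable, the point estimate and the composite are unchanged, and the low coverage depends on an interval that the SAP does not clearly choose. The 1% figure should not carry the argument; the shortfall at 4.8% and over 2–7% is enough. But SAP 3.1.3 is the section headed as the method for this endpoint and it is wrong as written. Following SAP 3.1 instead still leaves Wald open. The committee's remit may explain the TVR label but does not make it match the MACE definition.

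**Conclusion.** The concern holds, as something that should be fixed rather than a threat to the study. SAP 3.1.3 contradicts SAP 3.1, SAP 5.11 and Protocol 11.3.2, and the type of interval is nowhere specified.

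If a mean/SD or Wald interval results, the upper limit is about 2 percentage points too low at 5/100, the interval has zero width at 0/100, and coverage averages about 90% for true rates of 2–7%. These sizes assume n = 100 with complete data, a two-sided 95% interval and the illustrative event rates. If SAP 3.1 is followed with an exact interval, the problem does not arise.

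The TVR label is a separate error of definition. It affects only the component table, and its size cannot be derived from the documents.

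**What to change.** Replace SAP 3.1.3 with:

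> 30-day MACE will be reported as n/N and % with a two-sided 95% exact (Clopper-Pearson) CI.

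Name the same interval in SAP 3.2 for technical success and in SAP 3.3 for the binary secondary endpoints. For technical success this is for consistency, since the numbers barely move. For the secondary endpoints it matters if the events are rare.

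In SAP 3.1, change the third component to ischemia-driven TLR (CEC-adjudicated). If TVR is wanted, show it in a separate row marked as not part of MACE.

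The cost is SAP wording only, with no new data; SAP 5.12 already provides for documented changes before the analyses are run. The reported upper limit becomes less favourable (11.3% instead of about 9.3% at 5/100). The exact interval is conservative: it covers 95.1–99.5% over true rates of 1–8.5%. Wilson is shorter and averages close to 95%, but it covers 92.1% at 1% and 93.1% at 8.5%, and is below 95% on about 31% of the 1–8.5% range.
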